6.1.15 Dabrafenib + Trametinib Dose Modification for Pneumonitis

Pneumonitis has been observed in patients receiving trametinib in combination with dabrafenib. To reduce the risk of pneumonitis, patients will be monitored closely for symptoms, evaluated with imaging and functional tests when appropriate.

Table 6-13: Dabrafenib-Trametinib Treatment Modification for Pneumonitis

CTCAE Grade	Adverse Event Management	Action and Dose Modification
Grade 1	
 CT scan (high-resolution with lung windows) recommended. Clinical evaluation and laboratory work-up for infection. Monitoring of oxygenation via pulse-oximetry recommended. Consultation with pulmonologist recommended. 	Continue study treatment at current dose
Grade 2	
 CT scan (high-resolution with lung windows). Clinical evaluation and laboratory work-up for infection. Consult pulmonologist. Pulmonary function tests: If $<$ normal, repeat every 8 weeks until \geq normal. Bronchoscopy with biopsy and/or BAL recommended Symptomatic therapy including corticosteroids if clinically indicated. 	
 Interrupt trametinib until recovery to grade ≤ 1. Restart with trametinib reduced by one dose level. Escalation to previous dose level after 4 weeks and consultation with the CTEP Medical Monitor may be considered. If no recovery to grade ≤ 1 within 4 weeks, permanently discontinue trametinib.
Grade 3	
 Same as grade 2 	
 Interrupt study treatment until recovery to grade ≤ 1. Resumption of trametinib at one dose level reduction may be considered after consultation with the CTEP Medical Monitor If no recovery to grade ≤ 1 within 4 weeks, permanently discontinue trametinib.
Grade 4	
 Same as grade 2 	Permanently discontinue trametinib.

6.1.16 Dabrafenib or Dabrafenib + Trametinib Dose Modification for Liver Chemistry Changes

Table 6-14: Dabrafenib or Dabrafenib-Trametinib Dose Modification for Liver Chemistry Changes

Event	Treatment modifications and assessment/monitoring

 ALT ≥ 3x ULN but <5x ULN and TB <2x ULN, without symptoms considered related to liver injury or hypersensitivity and who can be monitored weekly for 4 weeks 	
 May continue study treatment. Report as SAE if CTEP-AERS reporting criteria is met. If liver chemistry stopping criteria are met any time, proceed as described below. 
MONITORING: Repeat LFT (ALT, AST, ALK, bilirubin) until they return to normal/baseline or stabilize (LFT may be every 2 weeks after 4 weeks if ALT <3x ULN and TB <2 ULN).


Criteria for discontinuing study drug: When any of the liver stopping criteria below is met, discontinue trametinib and dabrafenib
 
 ALT ≥ 3xULN and bilirubin ≥ 2x ULN or $>35\%$ direct bilirubin^{1,2} ALT ≥ 3xULN and INR >1.5, if INR measured² (INR threshold does not apply if subject is on anticoagulant) ALT ≥ 5x ULN ALT ≥ 3x ULN persists for ≥ 4 weeks ALT ≥ 3x ULN and cannot be monitored weekly for 4 weeks ALT ≥ 3x ULN associated with symptoms³ (new or worsening) believed to be related to liver injury or hypersensitivity 	
 Immediately discontinue study treatment. Do not restart/rechallenge unless approved by CTEP medical monitor. [Do not include for single-dose studies.] Report as SAE if: 1) CTEP-AERS reporting criteria are met, or 2) patients meet criteria 1-2. Perform liver event ASSESSMENT AND WORKUP (see below). Monitor the subject until liver chemistries resolve, stabilize, or return to baseline (see MONITORING below). If applicable, provide details on required follow up assessments (e.g., follow up for overall survival or disease recurrence or progression). [Do not include for single-dose studies] 
MONITORING: In patients stopping for criteria 1-2 (with abnormal TB and INR, indicating potentially more significant liver toxicities):
 
 Repeat liver chemistries (ALT, AST, ALK, bilirubin) and perform liver event follow-up assessments within 24 hours. Monitor subjects twice weekly until LFT return to normal/baseline or stabilize. A specialist or hepatology consultation is recommended. 
In patients stopping for criteria 2-6:
 
 Repeat LFT and perform liver event follow up assessments within 24-72 hours Monitor subjects weekly until LFTs return to normal/baseline or stabilize. 
ASSESSMENT and WORKUP:
 
 Viral hepatitis serology.⁴ If possible, obtain blood sample for PK analysis.⁵ Serum CPK and LDH. Fractionate bilirubin, if total bilirubin ≥ 2x ULN. CBC with differential to assess eosinophilia. Record clinical symptoms of liver injury, or hypersensitivity on AE CRF. Record concomitant medications (including acetaminophen, herbal

Event	Treatment modifications and assessment/monitoring
	
remedies, other over the counter medications).
 
 Record alcohol use. 
Additional work up for patient stopping for criteria 1-2 (with abnormal TB and INR, indicating potentially more significant liver toxicities):
 
 Anti-nuclear antibody, anti-smooth muscle antibody, Type 1 anti-liver kidney microsomal antibodies, and quantitative total immunoglobulin G (IgG or gamma globulins). Serum acetaminophen adduct HPLC assay (in subjects with likely acetaminophen use in the preceding). If there is underlying chronic hepatitis B (e.g. positive hepatitis B surface antigen): quantitative hepatitis B DNA and hepatitis delta antibody.⁶ Liver imaging (ultrasound, MRI, CT) and /or liver biopsy.

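### In Table 6-14, liver stopping criterion 2 (raised ALT with raised INR) falls under two monitoring headings with different timings, and nothing says which governs

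*Combined protocol and SAP*

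**What the plan says.** Table 6-14 in Section 6.1.16 lists six numbered criteria, any one of which requires dabrafenib and trametinib to be stopped. All six involve ALT. The second is ALT at least 3x ULN "and INR >1.5, if INR measured", and the INR threshold is waived for patients on an anticoagulant.

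The monitoring text in the same table then has two blocks.

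- The first is headed "In patients stopping for criteria 1-2 (with abnormal TB and INR, indicating potentially more significant liver toxicities". Its instructions are to repeat the liver chemistries and "perform liver event follow-up assessments within 24 hours", then "Monitor subjects twice weekly until LFT return to normal/baseline or stabilize". It adds: "A specialist or hepatology consultation is recommended".
- The second is headed "In patients stopping for criteria 2-6". Its instructions are "Repeat LFT and perform liver event follow up assessments within 24-72 hours" and "Monitor subjects weekly until LFTs return to normal/baseline or stabilize". It has no line on consultation.

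Two other parts of the table use a grouping of criteria. The SAE rule requires a report for patients meeting criterion 1 or 2, and the additional work-up (autoantibodies, liver imaging or biopsy, and so on) is for patients stopping under criterion 1 or 2.

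**The concern.** The two headings share criterion 2. A patient who stops because of raised ALT with raised INR is therefore assigned to both blocks, and the blocks differ in the time to first recheck, the frequency of continued monitoring and the advice to consult. Neither Table 6-14 nor any other section of the protocol says which block prevails.

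What is at stake is patient safety and consistency between sites. The table's own heading marks criteria 1 and 2 as the more worrying group. A site that reads the second heading literally would still be following the protocol if it gave such a patient the slower schedule. In a multicenter study, two sites could handle the same event differently, and a monitor could not say that either had deviated.

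**Working it through.** No sample-size, power or error-rate figure is involved, and the plan states no figure to reproduce. The check is to map each criterion to every monitoring block whose stated range includes it, and then to compare the timings.

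**Step 1. Mapping.** Block A is the heading for criteria 1-2 and block B the heading for criteria 2-6.

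| Stopping criterion (Table 6-14, paraphrased) | Block A | Block B |
|---|---|---|
| 1. ALT at least 3x ULN with raised bilirubin | yes | no |
| 2. ALT at least 3x ULN with INR above 1.5 | yes | yes |
| 3. ALT at least 5x ULN | no | yes |
| 4. ALT at least 3x ULN lasting 4 weeks or more | no | yes |
| 5. ALT at least 3x ULN, weekly monitoring not possible | no | yes |
| 6. ALT at least 3x ULN with liver or hypersensitivity symptoms | no | yes |

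The intersection of {1, 2} and {2, 3, 4, 5, 6} is {2}. Only criterion 2 is assigned twice.

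**Step 2. Size of the difference for a criterion 2 patient.**

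| Item | Block A | Block B | Difference |
|---|---|---|---|
| Latest time of first recheck | 24 h | 72 h | 72 - 24 = 48 h |
| Continuing checks per week | 2 | 1 | 1/2 = half as often |
| Consultation recommended | yes | not stated | absent from B |

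The 48 hours is a maximum: it compares the outer limits of the two windows.

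**Step 3. Is this a numbering accident of the PDF?** It does not look like one. There are exactly six criteria, which matches the upper end of the second range. The reference to bilirubin and INR in the first heading matches the content of criteria 1 and 2. The table's footnotes are not in the text I could read, but their marks attach to criteria and work-up items, not to either monitoring heading.

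**Step 4. Consistency within the table.** Criteria 1 and 2 are paired three times: in the first monitoring heading, in the SAE rule and in the additional work-up. The second monitoring heading is the only place that also puts criterion 2 with criteria 3 to 6.

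**Step 5. Patients who meet more than one criterion.** A patient with INR above 1.5 and ALT at least 5x ULN meets criteria 2 and 3. If criterion 2 were placed only with criterion 1, that patient would still fall under both blocks. The same holds now for a patient meeting criteria 1 and 3. Removing the overlap between the headings therefore does not by itself settle which schedule applies.

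**The case against.** The strongest reply is that this is a typographical slip that the rest of the table largely neutralizes. Criteria 1 and 2 are paired three times, twice with an explicit reference to bilirubin and INR, so a careful reader has a strong hint of how criterion 2 is grouped. That stands, and it lowers the chance that a site would use only the slower block. It does not remove the second heading, which is current, operative text.

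A reader might infer that the two schedules cannot both be applied to one patient. The documents do not support that. A recheck within 24 hours also meets the 72-hour outer limit, and twice-weekly checks also satisfy a weekly requirement. A site on the faster schedule stays within the outer limits of both blocks. The problem is that the reverse is not true, and the text permits the slower choice.

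A reader might also infer an effect on dose-limiting toxicity, because Section 5.2 exempts certain grade 3 laboratory abnormalities that return to baseline within 7 days, and sparser checks could miss the recovery. This is not demonstrated. INR is not on that list. Only a patient in cycle 1 who also had a listed grade 3 abnormality, such as ALT, could be affected, and the Study Calendar (Section 10) also schedules chemistry on Days 8 and 15 of cycle 1 for patients receiving AT13387. Nothing here bears on the operating characteristics of the 3+3 design.

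Finally, exposure is narrow. Criterion 2 needs a measured INR, the calendar schedules coagulation tests only at baseline and then as indicated, and patients on anticoagulants are outside the INR threshold. This stands and limits how many patients are likely to be affected.

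**Conclusion.** The point holds as a minor but genuine inconsistency in operative safety text. Criterion 2 is assigned to two monitoring schedules with no rule of precedence. The consequence, if a site follows the slower block, is a first recheck up to 48 hours later, half as many continuing checks, and no prompt for the recommended consultation.

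Stopping dabrafenib and trametinib, the bar on restarting without medical monitor approval, SAE reporting and the additional work-up for criterion 2 do not depend on the monitoring headings and are unaffected. No planned analysis changes. The conclusion assumes that the table's footnotes, which I could not read, contain no precedence rule; their marks give no sign of one. The documents do not give the expected number of criterion 2 events, so I make no estimate of it.

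**What to change.** Reconcile the two monitoring headings in Table 6-14 so that each of the six stopping criteria belongs to one monitoring group. Add one sentence stating which schedule governs when a patient meets criteria from both groups at the same time. The sponsor's clinical team should decide the assignment and the precedence rule; this review does not say which schedule is right for criterion 2.

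Whichever way it is decided, the SAE rule and the additional work-up heading should be read against the result, since both now pair criteria 1 and 2. The cost is a small text edit that can go into the next amendment, with no effect on sample size, the dose-escalation rules or the analyses. Sites would need to be told of the clarification.

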6.1.17 Dabrafenib or Dabrafenib-Trametinib Dose Modification for Venous Thromembolism (VTE)

	Dabrafenib	Trametinib (When Used in Combination)
Uncomplicated DVT or PE	Do not modify the dose.	Withhold trametinib for up to 3 weeks. 
 If improved to Grade 0-1, resume at a lower dose level. If not improved, permanently discontinue.
Life Threatening PE	Permanently discontinue dabrafenib	Permanently discontinue trametinib.

6.2 AT13387 Dose modifications

AT13387 dosing may be reduced in the setting of toxicity. The below table denotes the possible dose levels based on the dose escalation schema.

Current Dose	If Dose Reduction Required	Reduce To
260 mg/m ² days 1, 8, and 15	→	220 mg/m ² days 1, 8, and 15
220 mg/m ² days 1, 8, and 15	→	180 mg/m ² days 1, 8, and 15
180 mg/m ² days 1, 8, and 15	→	150 mg/m ² days 1, 8, and 15
150 mg/m ² days 1, 8, and 15	→	Discontinue AT13387

Further dose modifications to 120 mg days 1, 8, and 15 are permitted at the discretion of the Investigator but should be discussed with CTEP and the study sponsors. In the event that dabrafenib, trametinib, or both agents need to be discontinued due to toxicity reasons, treatment with AT13387 may continue at the discretion of the investigator until time of disease progression.

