5. TREATMENT PLAN

5.1 Agent Administration

Treatment will be administered on an outpatient basis. A cycle of treatment will be 28 days in length. IV administration will begin approximately the same time oral agents are dosed, but not more than 10 minutes after oral agents are taken. For Cycle days 8 and 15, patients will be instructed to bring oral agents with them to be given in the clinic. Patients are asked to maintain a medication diary for recording each dose of Dabrafenib and Trametinib (Appendix D).

Reported adverse events and potential risks are described in Section 7. Appropriate dose modifications are described in Section 6. No investigational or commercial agents or therapies other than those described below may be administered with the intent to treat the patient's malignancy. The patient will be requested to maintain a medication diary of each dose of medication. The medication diary (Appendix D) and pill bottles will be returned to clinic staff at the end of each course. To document compliance, a pill count will be performed of all unused pills.

Dosing levels for the study are listed below in Table 5.1. Dose level 1 will be the first dose level. Intrapatient dose escalation will be allowed when safe and feasible once the next higher dose level has been cleared. Additional, intermediate dose levels may be enrolled under the following

conditions:

- 1) Toxicity is seen at a dose level where dose modification is necessary and the prior, lower dose level was treated without DLT or analysis of the PK data suggests that an intermediate dose would be appropriate;
- 2) An intermediate dose is conceivable based on the size of pills and nature of the toxicity at the higher dose;
- 3) Consensus agreement is made between investigators, industry sponsors, and CTEP;
- 4) CTEP and IRB approval of an amendment to the protocol that clearly describes the rationale for and the logistics of the intermediate dose level.

Table 5.1 Dose Escalation Levels for Phase I Study

Dose Level	Dabrafenib [BID/PO]	Trametinib [QD/PO]	AT13387 [D1,8,15/IV]
-1	75 mg	1 mg	180 mg/m ²
1	150 mg	1 mg	180 mg/m ²
2	150 mg	2 mg	180 mg/m ²
3	150 mg	2 mg	220 mg/m ²
4	150 mg	2 mg	260 mg/m ²

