5.1.3 AT13387

AT13387 is dosed in mg/m² using institutional standard of practice for dose calculations. AT13387 is administered via Infusion. Infuse over 1 hour through a central line or a well-defined peripheral vein (Note: an in-line filter is NOT required). If use a peripheral line, be sure to aspirate venous blood prior to starting the infusion. Check the

infusion site every 15 minutes and change the site of infusion should evidence of swelling or discoloration is observed. If AT13387 cannot be administered on Cycle Day 8 or 15, the dose will be skipped and not delayed.

If patient experiences pain along the infusion site, slow the infusion rate (i.e. > 1 hour duration) and/or infuse D5W through a “Y” connector. The additional volume of D5W dilutes AT13387 concentration at the local site of the infusion and alleviates the irritation.

In the event that trametinib, dabrafenib, or both agents need to be discontinued due to toxicity reasons, treatment with AT13387 may continue at the discretion of the investigator until time of disease progression.

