6.2.1.1 Dose Reduction and Interruption

Table 6-15: AT13387 Dose Modification for Toxicities Not Specified in Subsequent Sections

CTCAE Grade	Action and Dose Modification
Grade 1	
Continue study treatment at same dose level (no dose modification).Monitor closely.Provide supportive care according to institutional standards.
Grade 2 (Tolerable)	
Interrupt study treatment if clinically indicated.Monitor closely.Provide supportive care according to institutional standards.When toxicity resolves to grade 1 or baseline, restart study treatment at current dose level.
Grade 2 (Intolerable) Grade 3	
Interrupt study treatment.Monitor closely.Provide supportive care according to institutional standards.When toxicity resolves to grade 1 or baseline, restart study treatment reduced by one dose level.If the grade 3 toxicity recurs, interrupt study treatment.When toxicity resolves to grade 1 or baseline, restart study treatment reduced by another dose level.
Grade 4	
Interrupt study treatment.Monitor closely.Provide supportive care according to institutional standards.Restart with study treatment reduced by one dose level once toxicity resolves to grade 1 or baseline.If the grade 4 toxicity recurs, either permanently discontinue study treatment or, if the patient is clinically benefiting, discuss continuation of study treatment with the CTEP Medical Monitor.
In the event of abdominal pain or suspected pancreatitis, amylase and lipase laboratory samples should be collected for confirmation of the diagnosis.	

Dose reductions for QTc elevations

A 12-lead EKG will be performed in triplicate prior to the start of each AT13387 infusion. If a subject's QTc is >480 msec but ≤ 500 msec, the infusion will be withheld until the subject's QTc has decreased to ≤ 480 msec and then the subject may be dosed at the same dose level. If a subject's QTc is ≥ 500 msec, the treatment will be withheld until the subject's QTc has decreased to <480 msec and then the subject will be dosed at one dose level below their assigned treatment.

Dose modifications for ocular toxicity

While ocular toxicity is an adverse event of special interest, dose reductions and modifications will be made based on the table above (Table 6-13). Additionally, patients will be required to

have an ophthalmology visit within 24 hours of first event of visual disturbance.

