8.1.3 AT13387

Chemical Name: (2,4-dihydroxy-5-isopropyl-phenyl)-[5-(4-methyl-piperazin-1-ylmethyl)-1,3-dihydro-isoindol-2-yl]-methanone, *L*-lactic acid salt

Other Name: AT13387AU, Onalespib

Classification: Heat shock protein 90 (HSP90) inhibitor

Molecular Formula: C₂₄H₃₁N₃O₃.C₃H₆O₃

M.W.: 499.61

Mode of Action: AT13387 is a synthetic non-ansamycin small molecule that inhibits heat shock protein 90 (HSP90). HSP90 seems to affect multiple aberrant signaling pathways and therefore may be of clinical benefit in several cancer treatments.

How Supplied: AT13387 is supplied by Astex Pharmaceuticals Inc. and distributed by CTEP, NCI as a 265-mg free base equivalent (*L*-lactic acid salt) vial, containing white to off-white lyophilized powder. The agent is formulated in **pH 5.0 (red cap)**.

Preparation: Reconstitute the 265-mg lyophilized powder with 10 mL of Sterile Water for Injection (SWFI) resulting in 25.7 mg/mL concentration (10.3 mL total volume). A sticky mass will be formed. Vigorously shake the vial. Agitate until the contents are fully dissolved (about 5 minutes). Leave the diluted vial at ambient temperature for 15-30 minutes to allow any foam to dissipate. If not used immediately, store the reconstituted vial(s) at 2⁰ to 8⁰ C not to exceed 8 hours.

Withdraw the calculated dose of AT13387 and further dilute it in 250 mL of D5W or 0.9% NS. The prepared IV solution is compatible in PVC or non-PVC infusion bags.

Store the prepared IV solution at 2⁰ to 8⁰ C (not to exceed 8 hours) if not used immediately. When removed from the refrigerator, allows the prepared IV solution to sit at room temperature between 15 to 30 minutes before administering to patients. The prepared IV solution must be used within 8 hours -i.e., from the time the drug vial is diluted to the time the IV administration is complete. Protection from light during the infusion period is not required.

Storage: Store the intact vials at 15⁰ to 25°C (59 to 77°F). Protect from light.

If a storage temperature excursion is identified, promptly return AT13387 to 15⁰ to 25°C (59 to 77°F) and quarantine the supplies. Provide a detailed report of the excursion (including documentation of temperature monitoring and duration of the excursion) to [contact] for determination of suitability.

Stability: Shelf life surveillance of the intact vials is ongoing.

Route of Administration: Intravenous

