13. STATISTICAL CONSIDERATIONS

13.1 Study Design/Endpoints

This is a phase I trial of the combination of dabrafenib, trametinib, and AT13387 in patients with BRAF-mutant advanced solid tumors. The primary objective of the study is to determine the maximum tolerated dose (MTD) of the combination; secondary objectives will provide preliminary estimates of efficacy and toxicity. The escalation and stopping rules imply that the incidence rate for DLT will be less than 33% at the MTD. Following the identification of the MTD, an additional 14 patients will be enrolled in a dose expansion cohort at the MTD.

Toxicities and lab values will be graded according to the NCI Common Toxicity Criteria for Adverse Events (v4.0). Dose-limiting toxicities will be scored and will be defined as in Section 5.2.

Dose escalation will use a standard “3+3” approach, beginning in dose level 1, with dosing and rules for escalation and de-escalation described in the tables below. Tolerability assessments will be based on cycle 1 alone. The MTD is defined as the highest dose level at which 0 or 1 of six patients has experienced a DLT. If an excessive number of toxicities occur at the initial dose level 1, the dose will be reduced to the fall-back dose of -1. If dose level -1 has excessive toxicity, the study will stop.

Dose Level	Dabrafenib [BID/PO]	Trametinib [QD/PO]	AT13387 [D1,8,15/IV]
-1	75 mg	1 mg	180 mg/m ²
1	150 mg	1 mg	180 mg/m ²
2	150 mg	2 mg	180 mg/m ²
3	150 mg	2 mg	220 mg/m ²
4	150 mg	2 mg	260 mg/m ²

Number of Patients with DLT at a Given Dose Level	Dose Escalation Rule
0 out of 3	Proceed to the next dose level and enroll 3 patients
1 out of 3	Enroll and treat 3 additional patients at this dose level
	Dose escalation will be stopped. The MTD will be one dose below this dose

≥ 2 out of 3	level. Three (3) additional patients will be entered at the next lower dose level if only 3 patients were treated previously at that dose.
1 out of 6	Proceed to the next dose level.
≥ 2 out of 6	se escalation will be stopped. The MTD will be one dose below this dose level. Three (3) additional patients will be entered at the next lower dose level if only 3 patients were treated previously at that dose.

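### Section 6.2 allows a further AT13387 reduction to a flat 120 mg, although the drug is dosed per square metre everywhere else; the /m² appears to be missing

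*Combined protocol and SAP*

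**What the plan says.** Section 5.1.3 gives the general rule for the unit: "AT13387 is dosed in mg/m² using institutional standard of practice for dose calculations". Table 5.1 lists AT13387 at 180, 220 and 260 mg/m² across dose levels -1 to 4, and the dose table in section 13.1 repeats those values. The reduction table in section 6.2 runs from 260 to 220, 180 and 150 mg/m², each on days 1, 8 and 15, and gives discontinuation as the step after 150 mg/m².

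Directly below that table comes a discretionary exception: "modifications to 120 mg days 1, 8, and 15 are permitted at the discretion of the Investigator but should be discussed with CTEP". The sponsors are to be part of that discussion too. The 120 mg carries no /m².

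The preparation text in section 8.1.3 tells the pharmacy: "Withdraw the calculated dose of AT13387 and further dilute it in 250 mL of D5W or 0.9% NS". It does not say how the dose is calculated, so the unit has to come from the dosing sections.

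**The concern.** The sentence is an operative instruction for an intravenous drug and the only place in the protocol where this dose is set. No table row stands behind it to supply the unit, because the table itself stops the drug after 150 mg/m². As written it states a fixed dose, in conflict with section 5.1.3 and with the rows immediately above.

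A flat figure would not necessarily look wrong to a reader of section 6. The ladders for dabrafenib and trametinib in section 6.1 are in flat milligrams, and a fixed low dose could be taken as deliberate for a patient who would otherwise stop treatment. The consequence would be a dose well below the one intended, or different doses at different sites for the same protocol step.

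**Working it through.** **Unit comparison**

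| Place | AT13387 dose | Unit |
|---|---|---|
| Section 5.1.3, general rule | – | mg/m² |
| Table 5.1 | 180, 180, 180, 220, 260 | mg/m² |
| Section 13.1 dose table | 180, 180, 180, 220, 260 | mg/m² |
| Section 6.2 table, dosed rows | 260, 220, 180, 150 | mg/m² |
| Section 2.2.3.3, earlier twice-weekly regimen | 120 | mg/m² |
| Section 6.2, sentence under the table | 120 | mg |

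Only the last line departs from mg/m². The /m² is intact in every dosed cell of the table just above that sentence, so its loss in text extraction is unlikely. The schema table at the front of the protocol was not available to check.

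**Does 120 mg/m² fit the ladder?** The size of a step is 1 − new/old:

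- 260 to 220: 1 − 220/260 = 15.4%
- 220 to 180: 1 − 180/220 = 18.2%
- 180 to 150: 1 − 150/180 = 16.7%
- 150 to 120, if per m²: 1 − 120/150 = 20.0%

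It fits.

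**What the literal reading gives.** Body surface area (BSA) is not stated in the protocol; 1.5 to 2.4 m² is assumed. The formulas are:

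- literal dose per m² = 120/BSA
- cut from 150 mg/m² = 1 − 120/(150 × BSA)
- intended total = 120 × BSA
- literal/intended = 120/(120 × BSA) = 1/BSA

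| BSA (m²) | Flat 120 mg, per m² | Cut from 150 mg/m² | Intended total (mg) | Literal/intended |
|---|---|---|---|---|
| 1.5 | 80.0 | 46.7% | 180 | 66.7% |
| 1.8 | 66.7 | 55.6% | 216 | 55.6% |
| 2.0 | 60.0 | 60.0% | 240 | 50.0% |
| 2.2 | 54.5 | 63.6% | 264 | 45.5% |
| 2.4 | 50.0 | 66.7% | 288 | 41.7% |

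**At the pharmacy.** Section 8.1.3 reconstitutes a 265 mg vial, "resulting in 25.7 mg/mL concentration (10.3 mL total volume"); 265/10.3 = 25.7 mg/mL reproduces that figure. The volumes drawn up are then:

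- flat 120 mg: 120/25.7 = 4.7 mL
- 120 mg/m² at 1.5 m²: 180/25.7 = 7.0 mL
- 120 mg/m² at 2.4 m²: 288/25.7 = 11.2 mL

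**How a patient reaches the step.** Dose levels -1, 1 and 2 all use 180 mg/m². The first reduction goes to 150 mg/m². If grade 3 toxicity recurs, Table 6-15 says to "restart study treatment reduced by another dose level". The section 6.2 table then leads to discontinuation, so 120 is reached only if the investigator uses the discretionary sentence. From 220 or 260 mg/m² it lies one or two reductions further down.

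**The case against.** The strongest reply is that no one would misread the sentence. Section 5.1.3 fixes the unit for the drug, the sentence continues directly from a ladder in mg/m² with the same day schedule, the background gives 120 for this drug only per m², and nothing in the protocol sets up a flat-dose scheme. The step is also discretionary and comes with advice to talk first: "but should be discussed with CTEP and the study sponsors". An error would run towards under-dosing, in patients who have not tolerated 150 mg/m² and would otherwise stop, so it is not an overdose hazard. The percentages apply only if the sentence is followed literally, and they move with the assumed BSA: an upper limit of 2.2 m² instead of 2.4 m² lowers the largest cut from 67% to 64%.

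Most of this stands, and it is why the point is minor. The intended dose can be recovered from context and the practical risk is small. It is also fair that Table 6-15 alone does not bring a patient to 120, and the protocol gives no basis for estimating how many patients would get there. But the discussion is advised rather than required, and neither it nor the general unit rule changes the number printed in the one sentence that sets this dose.

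**Conclusion.** The concern holds. The sentence gives the wrong unit for an intravenous dose and conflicts with section 5.1.3 and with all three AT13387 dose tables that could be checked. If followed literally, it delivers 67% down to 42% of the dose very probably intended, and a 47% to 67% cut from 150 mg/m² instead of 20%. These figures assume a BSA of 1.5 to 2.4 m² and that 120 mg/m² was meant; the first is not in the protocol, and the second is an inference from the ladder and the unit rule.

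The effect is confined to possible under-dosing or inconsistent dosing in the few patients who take this step. The DLT definition, the MTD rule, the sample size and the analyses do not depend on it. Severity is minor.

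**What to change.** Ask the sponsor and CTEP to confirm the unit, then change 120 mg to 120 mg/m² in the sentence under the section 6.2 table. Optionally, show the conditional step from 150 to 120 mg/m² in the table itself, marked as discretionary. The cost is a one-word protocol correction, with no effect on design, sample size or analysis.
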